6.4. Trial Flow Diagram

7. OUTCOME MEASURES

7.1. Primary Outcome

Definition

Following the above Theory of Change, we are primarily interested in measuring potential changes in participants' housing outcomes. Our primary outcome measure will therefore be the number of days out of the 360 days after they were randomised that a person is in secure accommodation. This main analysis will be conducted after the endline data collection 12 months after randomisation.

For this purpose, we will be assessing participants' housing stability and their perceived housing quality and satisfaction (see Annexes B and C). We deem it necessary to complement participants' housing history with questions regarding other relevant aspects of housing such as 1) affordability, 2) choice, independence, privacy, 3) suitability.

Instruments

Questions concerning participants' housing history have been adapted from the Residential Time Line Follow Back Inventory (Tsemberis, S. et al. (2007; see Annex B). Modifications have been mainly made to simplify and adapt the questions to the UK context. Similarly, minor modifications have been made to the OMRA tool, which includes questions about general satisfaction with housing, affordability, choice, independence, and privacy, and suitability.

When is it measured

Participants' data used in this analysis will be collected at three time points: baseline (prior to randomisation) and endline (12 months after randomisation). We will also collect these measures at 6 months after randomisation, and this will be included in our interim analyses.

 For whom is it measured All participants in the treatment and control groups will be surveyed by IFF.

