Where 1{.} is an indicator function that is equal to 1 if its argument is true and 0 otherwise.

Then the outcome variable is regressed on $E(d_i|B_i)$ with an OLS regression of the form:

$$Y_{ipt} = \alpha + \beta_1 Y_{ip0} + \beta_2 E(d_i | B_i) + \beta_3 X_i + \beta_4 P_p + u_i$$

Where the CACE estimator is β_2

Outcome imputation

We anticipate attrition between baseline, midline and endline data analysis. We will conduct missing data analysis as described below in 10.9, but given that every participant will complete the baseline survey, we primarily expect attrition in terms of outcomes, which will not be imputed under the missing data analysis. However, we will include sensitivity analysis which imputes outcomes between the two post-treatment data points where participants have missing data for one of these points but not the other. As such, if someone is missing data from midline but completes the endline data collection, we will impute their midline outcome measure as their endline outcome, and vice versa.

If exploratory analysis of the missingness mechanism satisfies the MAR assumption, the imputation of these points will be conducted with a dataset that incorporates all three time points to allow for the maximisation of all observed information in the process of imputation.

Following imputation, analysis will be conducted as previously described, for each post-treatment time point separately.

 For the main analyses, our primary outcome measure will be how many days out of the 360 after randomisation that a person is in secure accommodation. This measure will combine the measurement

taken at six months (midline) and that at 12 months, each of which will capture the prior 180 days. When someone completes the endline data but not the midline, they will be asked to recall the last 360 days. As a sensitivity analysis, we will conduct analysis just using the 180 days prior to the endline data collection as an outcome measure.

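### The midline/endline copy rule in 10.6 mixes a 180-day count with a 360-day count when it is applied to days in secure accommodation

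*Protocol*

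**What the plan says.** Protocol section 7.1 defines the primary housing outcome as "the number of days out of the 360 days after they were randomised that a person is in secure accommodation". Section 10.6 repeats the 360-day definition and says that it combines the measurement "taken at six months (midline) and that at 12 months, each of which will capture the prior 180 days". For those who miss midline it adds: "When someone completes the endline data but not the midline, they will be asked to recall the last 360 days".

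Under outcome imputation, section 10.6 also gives a rule for participants with one of the two follow-up waves missing: "if someone is missing data from midline but completes the endline data collection, we will impute their midline outcome measure as their endline outcome". The same copy is made in the opposite direction when endline is the missing wave. The section mentions no rescaling and exempts no outcome. It continues: "Following imputation, analysis will be conducted as previously described, for each post-treatment time point separately". Section 10.3 confirms that the same regression is run at midline and at endline.

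Three further provisions matter here:
- A count over only the last 180 days before endline appears in 10.6 as a separate sensitivity analysis, not as the endline outcome.
- If the data are judged missing at random (MAR), 10.6 says the imputation will use a dataset holding all three time points. It does not say how the day count is put on a common scale.
- Section 10.9 keeps complete cases as the main analysis. It plans re-runs with earlier outcomes and predictors of missingness added and, if the data are missing not at random (MNAR), a range of imputation models including multiple imputation within arm and last observation carried forward.

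**The concern.** Copying a value between waves is coherent only if both waves measure the same quantity on the same scale. That is true of the satisfaction scale and the secondary scales. It is not true of the day count, which can run from 0 to 180 at midline and from 0 to 360 at 12 months.

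An unscaled copy therefore enters a participant with midline only at roughly half of what their history implies, and a participant with endline only at up to twice what is possible. The forward copy is the one that matters for the 12-month estimate. If the arms differ in how many people are seen only at midline, the arm with more of them is pushed down. The check is meant to show how sensitive the result is to attrition, and it would then carry an attrition-related artefact of its own.

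**Working it through.** **Inputs from the protocol.** Each wave covers 180 days and the primary outcome covers 360 (7.1, 10.6). The copy rule applies in both directions without rescaling (10.6). The minimum detectable effect size (MDES) is 0.273 with 270 analysed, baseline correlation 0.6, two-sided alpha 0.05 and power 0.8 (9.1, Table 7).

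**Inputs not in the protocol, assumed.** The mean number of secure days in each half-year, the share of analysed participants with midline only in each arm, and the SD of the 360-day count. The 25% attrition in 9.2 does not supply the second of these, because it includes people missing at both follow-up waves, to whom the rule does not apply.

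**The plan's own figure.** MDES = (1.960 + 0.842) × √(1 − 0.6²) × √(4/270) = 2.802 × 0.8 × 0.1217 = 0.273. This agrees with Table 7. It is used below only as a yardstick.

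**Step 1: the copy for one person.** Take someone in secure accommodation for a constant share s of the time. The true midline count is 180s and the true 12-month count is 360s.

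| s | True midline | True 12-month | Midline copied to 12-month | 12-month copied to midline |
|---|---|---|---|---|
| 0.25 | 45 | 90 | 45 | 90 |
| 0.50 | 90 | 180 | 90 | 180 |
| 0.60 | 108 | 216 | 108 | 216 (impossible) |
| 0.75 | 135 | 270 | 135 | 270 (impossible) |
| 1.00 | 180 | 360 | 180 | 360 (impossible) |

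The forward copy is always half the constant-share value and cannot exceed 180. It is too low but possible. The backward copy is impossible for anyone with more than 180 secure days. Imputing the 180-day component and summing gives 180s + 180s = 360s, which always lies in range.

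**Step 2: effect on the 12-month comparison.** Write a for the first-half count and b for the second-half count. The true outcome is a + b and the forward copy enters a, so the shortfall per copied person is b. Let m_T and m_C be the midline-only shares in the intervention and control arms. With no true effect:

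spurious difference (intervention − control) = (m_C − m_T) × mean of b

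- 10% v 15%, mean b = 90: 0.05 × 90 = 4.5 days
- 10% v 20%, mean b = 90: 0.10 × 90 = 9 days
- 10% v 20%, mean b = 120: 0.10 × 120 = 12 days

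The sign reverses if the intervention arm has more midline-only participants.

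With equal shares m and half-year effects δ1 and δ2, the estimated effect is δ1 + δ2 − mδ2. If δ1 = δ2 the attenuation is m/2. At m = 15% that is 7.5%.

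**Step 3: yardstick.** At an assumed SD of 150 days the MDES is 0.273 × 150 = 41 days, so 4.5 to 12 days is 11% to 29% of it. At an assumed SD of 90 the MDES is 24.6 days and the range is 18% to 49%.

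**Step 4: simulated illustration.** Assumptions: 180-day counts with mean about 100 and SD about 60 before truncation to 0–180, and effects of 10 days in the first half and 20 in the second before truncation. With 20% copied, the 12-month effect falls from 26.7 to 23.3 days. Copying the 180-day component and then summing gives 25.0. Of the 3.4-day loss, 1.7 days come from assuming no change between halves and the other 1.7 from the units. In the midline re-analysis, 62–63% of the copied values exceed 180 and the effect rises from 9.0 to 12.4 days.

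**The case against.** The strongest reply is that the rule was meant for what each wave collects. Section 10.6 says of the two measurements "each of which will capture the prior 180 days", and the rule imputes between those two data points. On that reading, 150 of 180 is copied into the missing wave, the sum is 300 of 360, and no unit error arises. The authors may well have intended this, but the text does not say it. It copies the outcome, and the same section says "our primary outcome measure will be how many days out of the 360 after randomisation that a person is in secure accommodation". It treats the 180-day endline count as a separate analysis. The reading also leaves a conflict: a participant who misses midline but completes endline recalls 360 days, so their first-half count is already observed and nothing needs copying. Computational detail may properly sit in an analysis plan that is not shown, but this is a stated rule that fails for one outcome, not an omission.

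Much of the rest of the defence stands, and it rules out several stronger readings:

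- A reader might infer that the primary result is affected. It is not, because that analysis uses complete cases.
- A reader might infer that impossible values enter the 12-month outcome. They arise only when endline is copied back, and then the 12-month count is observed. They reach only the midline re-analysis.
- A reader might take this as the main protection against attrition, or think that model-based imputation is planned only under MAR. Section 10.9 lists other checks, with multiple imputation in its MNAR branch.
- A reader might conclude that the standard error must be too small. A single copy does ignore imputation uncertainty, but mixing the two scales also adds spread (in the simulation the outcome SD rose from 90.7 to 94.6), so the net direction is not shown.
- Copying has no unit fault for the satisfaction and secondary scales. Replacing it there would be a preference.

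**Conclusion.** The rule needs correcting for the day count, within this one sensitivity analysis. Followed literally, it halves the 12-month value of midline-only participants relative to a constant share and can give endline-only participants an impossible midline value.

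The arithmetic for a single participant needs no assumption beyond the protocol's two windows. The trial-level size does. About 4.5 to 12 spurious days requires no true effect, a second-half mean of 90 to 120 days and midline-only rates 5 to 10 points apart. About 7.5% attenuation requires equal 15% rates and equal half-year effects. The protocol gives none of these quantities, so they show the possible scale and do not forecast it. They do not support saying that the check would overturn or falsely confirm the primary result.

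**What to change.** Amend the outcome-imputation paragraph of 10.6 for days in secure accommodation:

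1. Define the first-half and second-half counts as separate 0–180 components. Impute only a missing component, then sum to 360.
2. Where midline is missing but the 360-day recall was completed, split that history at day 180 and use the observed first-half count. Nothing is imputed. Annex B as printed asks about six months at every wave, so confirm that the longer recall is fielded with dates that allow the split.
3. Where endline is missing, preferably impute the second-half component by multiple imputation within arm, from baseline, the observed component, charity partner, age and gender, so that imputation uncertainty is carried. Section 10.9 already plans this method in one branch. If copying is kept as a simple check, copy the 180-day component and not the total.
4. State that any last-observation-carried-forward run of the day count under 10.9 uses the same 180-day component.

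The scale outcomes need no change on this ground. The cost is one paragraph and a little code. Section 13.2 already provides for an addendum before analysis.

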8. DATA COLLECTION

8.1. Data collection methods

IFF Research will be collecting data for the evaluation by carrying out baseline, midline and endline surveys with all participants (both treatment and control).

Our data collection approach is based on the principle of ensuring choice and flexibility to participants. Recognising people's different preferences and needs, data collection will offer multiple channels, reminders and callbacks, multiple points of contact, and incentives for survey completion

The approach to data collection is the product of extensive co-creation between CHI, IFF Research, evaluators, delivery partners, and members of CHI's Lived Experience Panel. Particularly, the insights of the Lived Experience Panel have been instrumental in defining and refining our proposed approach.

Data will be collected primarily through an online (Computer Assisted Web Interview (CAWI)) survey hosted on IFF's Dimensions platform. If participants do not respond to the online survey invitation, then IFF will contact them by phone (Computer Assisted Telephone Interview - CATI) to complete the survey with an experienced telephone interviewer.

To facilitate administration of the surveys, delivery partners (and/or referral organisations they work with) will collect personal data from participants, including contact details. This sample data, including any updates to contact details over the life of the evaluation, will be shared with IFF on a rolling basis. IFF will provide delivery partners with a template outlining the data they need to collect and share.

Table 6: Data collection procedures and assessment timeline

Assessment point/Data Collection	Type of data	Data collection approach	
Contact details	Contact details	Referral organisations to collect this from participants and share with IFF on a rolling basis	
Baseline	Baseline characteristics, Primary and Secondary outcomes (pre-intervention), Demographics	Online (CAWI) / Phone (CATI) survey by IFF Research	
Midline (6 months after randomisation)	Secondary outcomes	Online (CAWI) / Phone (CATI) survey by IFF Research	
Endline (12 months after	Primary and secondary outcome	Online (CAWI) / Phone (CATI) survey by IFF	

randomisation)	Exploratory outcomes	Research
	Exploratory dateomics	

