- 12. Accommodation linked to your work or studies, for example student accommodation, military accommodation or accommodation linked to a business.

1b. When did you start living there? (best guess)

(day/month/year)

[Note: This should be a best guess. The interviewer could also prompt by asking about time of year the person lived there.

A suggestion used in previous studies is to have a calendar with days and month for participants to work backwards from where they are currently living.]

1c. Roughly, how long have you stayed there [did you stay there]? (best guess)

Number in (months) + (weeks) + (days)

[Note: This should be a best guess. The person does not need to fill in the three levels]

1d. Have you stayed in any other accommodation in the last 6-months?

Yes, No

[If yes, jump back to 1.a]

Source: Modified version of the Residential Timeline

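### The primary outcome counts days 1 to 360 from randomisation, but the two-recall rule and the six-month housing questionnaire do not exactly deliver that window

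*Protocol*

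**What the plan says.** **Definition.** Protocol section 7.1 sets the primary outcome as "the number of days out of the 360 days after they were randomised that a person is in secure accommodation". Section 10.6 repeats the same window.

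**Construction.** The rule for the main analysis appears in section 10.6, under outcome imputation. The measure combines the measurement "taken at six months (midline) and that at 12 months, each of which will capture the prior 180 days". A sensitivity analysis uses only the 180 days before endline.

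**Missed midline.** Section 10.6 adds: "When someone completes the endline data but not the midline, they will be asked to recall the last 360 days".

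**Instrument.** Annex B is the only housing-history questionnaire and is marked for baseline, midline and endline. It takes a best-guess start date (1b) and length (1c) for each stay. Item 1d decides whether to loop back to an earlier stay: "Have you stayed in any other accommodation in the last 6-months".

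**Schedule.** Table 6 lists only secondary outcomes at midline. Sections 4.1, 7.1 and 10.6 and Annex B all collect housing history then. Table 4 puts midline fieldwork in February to June 2025 and endline in August to December 2025, after enrolment over five months from August 2024 (section 6.3). Non-responders to the online invitation are followed up by phone (section 8.1). The protocol gives no interview window per participant and no rule for overlaps, gaps or days beyond day 360.

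**The concern.** The outcome is anchored to randomisation, while its two components are anchored to interview dates. Unless the interviews fall on exact days, some of days 1 to 360 are not covered, and some other days are counted twice or lie outside the period.

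This could matter because early and late days are not interchangeable. Everyone starts in temporary accommodation, and funds typically take 2 to 4 weeks from referral to being spent (section 4.1). Replacing early days by later ones therefore changes what is estimated.

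Separately, section 10.6 relies on a 360-day recall that the printed questionnaire does not ask for. A stay that is never elicited cannot be restored at the analysis stage.

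**Working it through.** **The plan's own figure.** Inputs from Table 7: two-sided alpha 0.05, power 0.8, pre/post correlation 0.6, effective N 270.

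MDES = (1.960 + 0.842) × √[(4/270) × (1 − 0.6²)] = 2.802 × 0.0974 = 0.273, as stated. The same formula gives 0.236 at N = 360 and 0.293 at N = 234, also as stated. The point does not depend on these figures.

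**Windows.** Let midline fall on day m and endline on day e after randomisation. The two recalls cover days m − 179 to m and days e − 179 to e. The target is days 1 to 360.

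- *Exact case*, m = 180 and e = 360: days 1–180 and 181–360. All 360 days are covered and none is counted twice.
- *Calendar 6 and 12 months*, for every randomisation date from 1 August to 31 December 2024: m is 181 to 184 and e is 365. Days missed at the start are m − 180 (1 to 4). Days missed between the windows are 185 − m (1 to 4). The sum is always 5. Days 361–365 are counted, which is 5 days beyond the period.

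**Assumed delays.** The documents give none, so these rows are illustrations around m = 182 and e = 365.

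| Midline shift (days) | Endline shift (days) | Missed of 1–360 | Counted twice | Counted beyond 360 |
|---|---|---|---|---|
| 0 | 0 | 5 | 0 | 5 |
| +30 | 0 | 32 | 27 | 5 |
| +60 | 0 | 62 | 57 | 5 |
| 0 | +30 | 35 | 0 | 35 |
| +30 | +30 | 35 | 0 | 35 |
| 0 | −14 | 11 | 11 | 0 |

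For the second row, m = 212, so the windows are days 33–212 and 186–365. Days 1–32 are missed and days 186–212 (27 days) are counted twice.

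**Missed midline.** With Annex B as printed, an endline on day 360 with a 180-day look-back asks about days 181–360, which is 180 days. An endline on day 365 with six months taken as 182 days asks about days 184–365, of which 177 lie in the period. With the promised 360-day recall, an endline on day 365 covers days 6–365 and misses 5 days. If that endline is 30 days late, 35 are missed.

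**Illustrations of consequence, all on assumed inputs.**

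- Take a midline 30 days late against exact days 180 and 360, with a secure share of 5% in month 1 and 30% in month 7. One person's count then moves by 30 × (0.30 − 0.05) = 7.5 days. If such lateness were 10 percentage points more common in one arm, the arm means would differ by 0.10 × 7.5 = 0.75 days.
- If 10% of 270 endline responders could not be scored, N = 243 and MDES = 2.802 × √[(4/243) × 0.64] = 0.288.

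**After the fix.** If the look-back reaches the last interview or randomisation, and the count stops at day 360, coverage is 360 of 360 with none doubled for any interview dates, provided endline falls on or after day 360.

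**The case against.** The strongest reply is that Annex B is a dated residential timeline. Items 1b and 1c give the start and length of each stay, so overlaps can be removed, and a stay reaching back past the look-back can be traced to its start. The word used in section 10.6 is combine, which does not require adding two totals, and the derivation could sit in an analysis plan that is not shown. Table 4's fieldwork periods follow enrolment at 6 and 12 months, which suggests interviews timed to each participant. If Annex B's six calendar months are used in place of 180 days, on-time interviews leave no gap and give 365 days, 5 too many. The sensitivity analysis on the last 180 days cannot double count.

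Most of this stands, and it makes the repair cheap. It does not remove the mismatch. The protocol itself states a rule of two 180-day look-backs and does not say that the dates will be used to align them. Nor do the dates help with a stay that item 1d never reaches.

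Three stronger readings are tempting, and the documents do not support them:

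- *Everyone who missed midline supplies only half the outcome.* The loss is limited to stays that ended before the six-month look-back. It also assumes that the explicit promise in section 10.6 is not carried into the fielded script.
- *Midline housing history is not collected.* Only Table 6 suggests this. Sections 4.1, 7.1 and 10.6 and Annex B say otherwise, so the row is a slip.
- *The treatment effect is materially biased.* The 7.5 days is one late person's shift, not a difference between arms, and should not be set against the MDES. With equal lateness, the shift cancels if the early-to-late change is the same in both arms. If the effect grows over the year it would not fully cancel, but the documents give no figure for either lateness or growth.

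**Conclusion.** The point holds as a specification fault in the primary outcome. The stated construction matches the stated definition only for interviews on exactly days 180 and 360, and the printed instrument does not contain the 360-day recall on which section 10.6 relies.

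The size that follows from the documents alone is small: 5 of 360 days misaligned when interviews are on schedule at calendar 6 and 12 months. Anything larger rests on assumed delays. The 7.5-day shift and the MDES of 0.288 are likewise illustrations under assumed secure shares and an assumed 10% without midline. Even 0.288 is below the 0.293 of Scenario C, whose sample size section 9.2 already judges sufficient. No material bias is shown.

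The point still merits action because it concerns how the primary outcome is computed, and stays that are not asked about cannot be recovered later.

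**What to change.** 1. **Derivation.** State that each participant's stays, from the 1b and 1c answers at all interviews, are placed on a calendar starting at the recorded randomisation date. Count each secure day from 1 to 360 once and stop at day 360. Say which report prevails where two interviews disagree, and how days are handled if endline falls before day 360.
2. **Endline routing.** Change the Annex B look-back at endline to run from the last interview, or from the randomisation date if midline was missed.
3. **Table 6.** Add the primary outcome to the midline row.
4. **Anchor date.** Section 5.2 randomises on submission of the baseline survey, whereas section 15.2 allows a week to withdraw before randomisation. Reconcile the two, since this could move day 1 by up to about 7 days.

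The cost is derivation code, one routing change and text edits. The downside is a slightly longer recall at endline for some participants. This protocol version is dated 17 June 2025 and endline fieldwork starts in August 2025, so at that version the script could still be changed. If fieldwork has passed, item 1 can still be applied to the dates collected, but stays that were not elicited remain missing and should be reported as such.
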